- Patients who didn't follow post-operative instructions.
- Patients who are not able to come for the follow-up appointments.

Follow up:

- Patients who strictly follow post-operative instructions will perform another sleep study after 3 months from the day of the surgery.
- Percentage of AHI reduction will be calculated which in turn indicates post-surgical improvement.

2. Matching criteria and allocation ratio

The patients will be randomly allocated to the intervention groups using computer-generated random numbers that will be performed by the main investigator ([name]). The patients will be allocated in a ratio of 1:1 (35 patients in each group).

The two groups will be equally clinically examined before surgical procedures. Then the decision of which group will be scanned with CBCT and which won't will be taken according to the randomized numbers placed in opaque sealed envelopes. The number will be picked by the main investigator ([name]).

The main investigator will be responsible for the generation of allocation sequence and will assign the patients to the 2 intervention groups. The main investigator will also be responsible for patient enrolment.

C) Variables

1. Details about variables

- Mean AHI reduction percentage.
- Level of Collapse of the upper respiratory airway.
- The volume of the upper respiratory airway.

2. Data sources and management

- The level of the collapse of the upper respiratory airway will be determined by an expert ENT surgeon with DISE.
- Radiographic assessment will be performed using the iCAT FLX V17-Series CBCT machine (Imaging Science International, ISI, PA, USA). Quick scan imaging protocol of 16cm x 13cm Field Of View (FOV) (120 KV, 5 mA, 2 sec) and 0.3 mm voxel size.
- Participants are required to wear a protective lead apron during scanning. The position of the X-ray tube will be adjusted to minimize the extent of scanning and to ensure the lowest radiation dose as much as possible. To prevent motion artifacts, participants will be instructed not to move their head, body, tongue, and jaws during scanning.
- Raw DICOM data from CBCT scanning will be checked to evaluate whether there were any motion artifacts in images at coronal, horizontal, and sagittal planes.
- CBCT scans at both ends of inspiration and expiration will be analyzed using Invivo5 software.

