- For the second outcome, CBCT images will be interpreted by three oral and maxillofacial radiologists independently; blinded from demographic data of the patients, DISE findings, and the results of each other.
- Each radiologist will evaluate the CBCT images for assessment of the level of collapse and assessment of the secondary outcomes. One radiologist will assess all the outcomes twice with more than 1month interval. Intra-observer and inter-observer variability of CBCT findings will be evaluated.

3. Addressing potential sources of bias

No source of bias. CBCT images will be interpreted by three oral and maxillofacial radiologists independently blinded from demographic data of the patients, DISE findings, and the results of each other.

D) Study size

1. Study size

This study aims to assess surgical improvement in OSA patients after imaging of upper Respiratory Airway using CBCT and DISE using mean AHI reduction percentage. According to the results of (**Pang et al. 2020**), the mean of AHI reduction percentage and the minimal clinically important difference estimated by the expert was 21.6. By adopting an alpha (α) level of 0.05 (5%) and a power of 80%, the predicted sample size is 35 per group with a total of 70. To compensate for losses during follow up, the sample will be

increased by 20% to be 84 participants in total. Sample size calculation was achieved using PS: Power and Sample Size Calculation software Version 3.1.2 (Vanderbilt University, Nashville, Tennessee, USA).

E) Quantitative variables

1. Handling of quantitative variables in the analyses

The volume of the upper respiratory airway will be determined and correlated with its level of collapse.

F) Statistical methods

1. Statistical methods

Data will be analyzed using SPSS (statistical package for social sciences) version 22. Qualitative data will be presented as number and percent, Quantitative data will be tested for normality by the Kolmogorov-Smirnov test then described as mean and standard deviation for normally distributed data and median and range for non-normally distributed. The appropriate statistical test will be applied according to the data type with the following suggested tests: Chi-Square for the categorical variable. Student t-test and Mann Whitney U test for continuous variables.

II. Ethics and dissemination:

a. Research ethics approval

The study protocol will be submitted to the Ethics committee in the Faculty of Dentistry, Cairo University for approval.

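### Must the plan be changed because level of collapse is read from both DISE and CBCT, and no correlation or reader-agreement statistic is named?

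*Combined protocol and SAP*

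**What the plan says.** Section C.1 lists three variables: AHI reduction percentage, level of collapse and airway volume. Section C.2 gives the source of the second: "The level of the collapse of the upper respiratory airway will be determined by an expert ENT surgeon with DISE". The same section then says "For the second outcome, CBCT images will be interpreted by three oral and maxillofacial radiologists independently", and "Each radiologist will evaluate the CBCT images for assessment of the level of collapse and assessment of the secondary outcomes". The readers are "blinded from demographic data of the patients, DISE findings, and the results of each other". One of them reads everything twice, and "Intra-observer and inter-observer variability of CBCT findings will be evaluated".

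Section A.1 has DISE done in both arms and scored by both LwPTL and VOTE. CBCT is done in the study arm only, once at each end of the breathing cycle. Section E announces one analysis: "The volume of the upper respiratory airway will be determined and correlated with its level of collapse". On tests, section F says "The appropriate statistical test will be applied according to the data type with the following suggested tests: Chi-Square for the categorical variable" and "Student t-test and Mann Whitney U test for continuous variables". The only other test it names is Kolmogorov-Smirnov, for normality.

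**The concern.** One variable appears to have two sources, and the single analysis that uses it does not say which applies. Every study-arm patient has a DISE rating and a CBCT rating, so both correlations can be computed and the preferred one reported afterwards.

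The choice could matter. With DISE, volume and collapse come from different methods and different observers. With CBCT, the same radiologist may read both from the same images, and the stated blinding does not hide a reader's own volume result. Error common to the two readings would then add to the correlation. The scan phase, the DISE classification and the rule for combining three readers are also open.

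Separately, the plan announces a correlation and a reader-variability analysis, but none of the four named tests measures either. Applied literally, the listed tests would serve reader variability badly.

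**Working it through.** **Text, side by side.** Sections A.1 and C.2 give a DISE rating by the surgeon in both arms. Section C.2 gives a CBCT rating by three radiologists in the study arm. Neither statement denies the other, and hiding DISE from the radiologists makes sense only if the two ratings are separate. That the second outcome means level of collapse is an inference from the order of the list in C.1; the sentence quoted above names collapse outright in any case.

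**Patients.** CBCT is the only volume source described, so the correlation uses the study arm whichever rating is chosen: 35 of 70, or 84/2 = 42 with the loss allowance. That DISE also covers the control arm makes no difference here.

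**Precision (Fisher z, n = 35).** For r = 0.30, the 95% interval is tanh(atanh(0.30) ± 1.96/√32) = tanh(0.310 ± 0.346), or about -0.04 to 0.58. The smallest r detectable with 80% power at two-sided 0.05 is tanh((1.960 + 0.842)/√32) = 0.46. Under either source this is a descriptive analysis.

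**Shared error (assumed model).** Let t be the variance share due to the true airway and s the share due to error common to volume and CBCT collapse. The latent correlation with volume is -t for DISE and -(t + s) for CBCT. Collapse is cut into thirds and Spearman is used with n = 35.

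| Shared error s | No true relation: p<0.05, DISE | No true relation: p<0.05, CBCT | t = 0.30: mean r, CBCT | t = 0.30: p<0.05, CBCT |
|---|---|---|---|---|
| 0.1 | 5% | 7% | -0.34 | 54% |
| 0.2 | 5% | 17% | -0.44 | 79% |
| 0.3 | 5% | 34% | -0.53 | 93% |
| 0.4 | 5% | 54% | -0.62 | 99% |

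With DISE and t = 0.30, the mean r is -0.26 and p<0.05 occurs in about 33%. With s = 0 the two sources agree. Repeat runs reproduce these figures to within simulation error.

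**If the shared error belongs to the reader.** Averaging three readers divides that variance by three. With no true relation, the latent correlation becomes -(s/3)/(1 - s + s/3): -0.04, -0.08, -0.13 and -0.18 for the four values of s. False significance then falls to about 6%, 7%, 9% and 15%. Only error belonging to the scan itself gives the full range in the table.

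**Choosing among results.** Two scan phases times two DISE classifications give 4 correlations; adding CBCT collapse gives 2 × 3 = 6. If the tests were independent, the chance of at least one false p<0.05 would be 1 - 0.95⁴ = 19% or 1 - 0.95⁶ = 26%. With correlated measures it is 11% to 16%, or 16% to 21%. These counts assume one overall grade per patient.

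**Is there such a grade?** Section A.1 describes DISE as identifying which structures contribute (larynx, palate, tongue, lateral walls), singly or together, and speaks of sites when it turns to CBCT. The plain reading is anatomical site, with several possible per patient. No three-grade score appears. Coded as collapse present or absent at a site, volume can be compared by t-test or Mann-Whitney, both of which section F lists.

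**Reader variability by the listed tests (n = 35).** An unpaired t-test detects a 0.3 SD reader bias at ICC 0.9 in 3% of studies, against 97% for a paired test. A chi-square on two readers' proportions, each 50%, finds no difference in 96% of studies at kappa 0. Those would be poor analyses, but no passage assigns either test to this purpose.

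**The case for a change.** The strongest argument for a change is that reading the ratings as parallel measurements does not settle which one section E uses. An invitation to choose a suitable test is also not prespecification. The volume correlation and reader variability are the only CBCT analyses announced in a radiology study, and one paragraph written before any scan is read would close off choice after the results are known.

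Part of this stands. Section E does not name its source, and no association or agreement statistic is named anywhere. What does not stand is the step from there to a required correction. Making DISE the main source, averaging volume readings and having different radiologists read volume and collapse are preferences among defensible options. A Spearman correlation and a weighted kappa need an ordered scale. They cannot be run until multi-site LwPTL or VOTE findings are reduced to one ordered value, and the documents give no rule for that. The sizes that make the issue look serious come from assumed shared error and from reader tests nobody proposed.

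**Conclusion.** No change to the plan follows. This is missing detail in secondary, descriptive analyses, and analysts would fill it sensibly. They would report DISE and CBCT collapse as separate ratings, say which one was set against volume, use an association measure that suits the coding, and use ICC or kappa for reader agreement. The wording of section F leaves room for all of that.

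The comparison of AHI reduction between arms is unaffected. The documents do not say whose CBCT reading reaches the surgeon, so they show no effect on the intervention. The false-significance range of 7% to 54% (about 6% to 15% with reader-specific error averaged over three readers) is hypothetical: it assumes 10% to 40% shared error and a single ordered grade. The 11% to 26% range for choosing among several correlations assumes one overall grade and that the smallest p-value is the one reported. The conclusion assumes that the volume correlation stays a supporting result. At n = 35 its 95% interval for r = 0.30 runs from about -0.04 to 0.58, so it could carry little more than that under either source.

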- Afterward, a proper physical examination will be performed including a thorough clinical examination of the oropharynx, nasopharynx, and hypopharynx to evaluate any anatomical abnormalities as impotency of the nasal airway, elongated soft palate or uvula, enlarged lingual tonsils, and any other pathological conditions of tongue, palate, and tonsils.
- Then, Polysomnography (PSG) (sleep study) will be performed to allow proper evaluation of normal and abnormal physiological sleep episodes. Apnea/Hypopnea Index (AHI) will be reported to detect the severity of OSA and patients were classified into mild (AHI = 5-14 / hour), moderate (AHI = 15-30 / hour) and severe (AHI >30 / hour) (*Maspero et al. 2015*).
- All patients in both groups will undergo upper airway surgery, DISE will be performed by the same ENT surgeon to detect the level of collapse in the upper airway which will be assessed by LwPTL and VOTE classifications, emphasizing on the primary structures contributing at upper airway collapse, either alone or in combination: the larynx, palate, tongue and pharyngeal lateral walls.
- Study group participants only will be scanned by CBCT twice; once at the end of inspiration and the other at the end of expiration while they are gently holding their breath for as long as possible. (*Woodson 2003*)
- In the study group, surgical procedures decision will be taken after appropriate assessment to sites of collapse in CBCT views at both ends of expiration and inspiration vies in combination to DISE.
- Finally, strict post-operative instructions will be given to patients of both groups.

2. Settings

This study will be carried out on patients attending outpatient clinics in the ENT department, Faculty of Medicine, Mansoura University, Egypt. CBCT scans of surgical candidates of OSA patients will be included

according to the proposed eligibility criteria.

B) Participants

1. Eligibility criteria and selection methods

Inclusion Criteria:

- Patients' age is more than 18 years old.
- Patients are indicated for upper respiratory airway surgery based on adequate history taking, proper clinical examination, and sleep study.
- Patients refusing non-surgical treatment procedures as Continuous Positive Airway Pressure (CPAP) treatment.
- Systemically medically free patients.

Exclusion Criteria:

- Patients who are refusing the surgical approach as a treatment option.
- Patients who have undergone previous surgeries in the upper respiratory airway.
- Pregnant women.

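### Does the plan need to name an agreement statistic for the repeated CBCT readings?

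*Combined protocol and SAP*

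**What the plan says.** Data sources and management (I.C.2) sets up a reader study within the CBCT arm. It states that "CBCT images will be interpreted by three oral and maxillofacial radiologists independently", without sight of demographic data, the DISE findings or one another's results. It continues: "Each radiologist will evaluate the CBCT images for assessment of the level of collapse and assessment of the secondary outcomes". For repeatability, "One radiologist will assess all the outcomes twice with more than 1month interval". The analytic commitment is one sentence: "Intra-observer and inter-observer variability of CBCT findings will be evaluated".

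Study design (I.A.1) fixes who is read: "Study group participants only will be scanned by CBCT twice; once at the end of inspiration and the other at the end of expiration". With 35 patients per group, or 42 if the total is "increased by 20% to be 84 participants in total" (Study size, I.D.1) and is split equally, that is 35 to 42 patients with two scans each.

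Statistical methods (I.F.1) is generic. "The appropriate statistical test will be applied according to the data type with the following suggested tests: Chi-Square for the categorical variable", followed by "Student t-test and Mann Whitney U test for continuous variables". Section I.E.1 adds a correlation, but between airway volume and level of collapse, not between readers. No section names an agreement statistic, a weighting, an ICC form, an interval or an acceptable level of agreement. The documents tie the LwPTL and VOTE classifications to DISE and give no grading scale for collapse on CBCT.

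**The concern.** Reader reliability matters here. The study calls itself a validity study, CBCT findings feed the surgical decision in one arm, and the bias section (I.C.3) rests on the three blinded readers. The reader exercise is the only planned check that the CBCT readings are reproducible.

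Two things look wrong at first. The named tests do not measure agreement: chi-square tests association, and the t-test and Mann-Whitney test compare location between independent groups. Also, kappa and ICC are families, so choosing them still leaves open the kappa weights, the ICC type and the treatment of two scans per patient. If those were settled after the readings had been seen, the more flattering form could be reported. Treating a patient's two scans as independent could also make the interval too narrow.

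**Working it through.** The plan states no agreement figure, so there is nothing to reproduce. The documents give no reader variances, prevalence or collapse scale, so all data below are assumed. They show how far the open choices could move a result and do not predict this trial's result.

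**1. The suggested tests cannot stand in for agreement.** Take 35 pairs on three grades with no pair agreeing (cells of 12, 12 and 11, all off the diagonal). Chi-square gives p of about 2e-14, while kappa is -0.50. For volume, two sets of 35 readings that are permutations of each other give a t-test p of 1.00 with a correlation of 0.09. An agreement statistic is therefore needed.

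**2. Kappa weights.** Assumed table, rows [8, 3, 0], [3, 7, 3], [0, 3, 8]; n = 35, margins 11, 13, 11. Kappa = 1 - (observed weighted disagreement)/(expected weighted disagreement).
- Unweighted: observed 12/35 = 0.343; expected 1 - (121 + 169 + 121)/1225 = 0.664; kappa 0.484.
- Linear: observed 12 × 0.5/35 = 0.171; expected 0.5 × 572/1225 + 242/1225 = 0.431; kappa 0.602.
- Quadratic: observed 12 × 0.25/35 = 0.086; expected 0.25 × 572/1225 + 242/1225 = 0.314; kappa 0.727.

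If collapse is scored yes/no, the three coincide and this point disappears.

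**3. ICC type for volume.** Let the consistency ICC be r, with total within-reader SD 1 and one reader shifted by d SD. The between-reader variance is d²/2 for two readings and d²/3 for three. The absolute-agreement ICC is then r/(1 + d²/2) or r/(1 + d²/3). With r = 0.90:

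| d | two readings | three readers |
|---|---|---|
| 0.3 | 0.90/1.045 = 0.861 | 0.90/1.030 = 0.874 |
| 0.5 | 0.90/1.125 = 0.800 | 0.90/1.083 = 0.831 |

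The consistency ICC stays at 0.90. If no reader is shifted (d = 0), the two types agree.

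**4. Two scans per patient.** The coverage formula for a mean, 2Φ(1.96/√(1 + ρ)) - 1, gives 95%, 89% and 83% at ρ = 0, 0.5 and 1. Here ρ must be the correlation of the two scans' contributions to the agreement statistic, not the correlation of a patient's two volumes. Simulation is more informative: 35 patients, two pooled scans, three readers, true ICC 0.9, one-way F interval.
- Volume correlation 0.5, independent reader errors: about 93%.
- Volume correlation 0.5, reader errors also correlated 0.5: about 92%.
- Volume correlation 1, independent reader errors: about 87%.
- Volumes and reader errors both perfectly correlated: about 83%.

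The cost of pooling is small unless the correlations are extreme, and the plan nowhere says that the scans will be pooled.

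**5. What depends on the figure.** The primary outcome is percentage reduction in AHI, taken from sleep studies. The sample size in I.D.1 is built on that outcome. No cut-off for agreement is set, and no step waits on the result.

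**The case for a change.** The strongest case for a change is that it would be cheap: a few sentences in I.F.1, with no new scans, readers or patients, and the form would be fixed before anyone sees the readings. Saying that any analyst would use kappa and ICC does not settle the matter, because steps 2 and 3 show the name alone leaves room for 0.48 to 0.73, or 0.80 to 0.90, on the same readings.

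The room to choose is real. But the movement is conditional: the kappa spread needs an ordinal scale, and the ICC spread needs a systematic difference between readers. The supportable statement is that the choice can change the figure, not that it will. The intervals at 35 to 42 patients would be just as wide if the plan had named its statistics, so precision is no argument here. Naming the forms would be good practice, but the plan is not in error without them. A report that gives the kappa weights, the ICC type and the unit of analysis lets readers judge the result.

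**Conclusion.** The observation is correct, but it does not call for a change. The plan fixes the part that cannot be repaired later: three independent blinded readers, and a second reading more than a month after the first. It leaves the summary statistic to the analyst. I.F.1 lets the method follow the type of data and calls its tests suggestions, so kappa and ICC are open to the analyst and no wrong method is prescribed.

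On assumed data, the open choices could move kappa between 0.48 and 0.73, and could move a consistency ICC of 0.90 to between 0.80 and 0.87 under absolute agreement. Pooling the two scans as independent would give coverage of about 93% at a volume correlation of 0.5 with independent reader errors. These sizes concern a secondary reliability report that has no threshold and no decision attached. The AHI comparison and the sample size are unaffected.

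This conclusion assumes that the analyst uses agreement measures for the repeat readings, as is customary, and reports which form was used. It would be different if the plan had assigned chi-square or t-tests to those readings, or had made a conclusion depend on a given level of agreement. It does neither.

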b. Protocol amendments

Any amendments in the protocol will be reported to the main and co-supervisors.

c. Informed consent

After discussing the treatment plan with the patient and educating the patient with all the data needed, an arabic consent form will be signed by the willing participants.

d. Confidentiality

- All study-related information will be stored securely.
- All reports, data, scans, and administrative forms will be identified by a coded ID (identification) number only to maintain participant confidentiality.
- All personal data that contain names or other identifiers including age, sex, identification number, address, phone number, work address, and any other information will be stored separately from the study records and identified by a code number.

e. Declaration of interest

There is no conflict of interest.

f. Access to data

Investigator, Co-supervisors, and main supervisor will have access to the final trial data set .

g. Dissemination policy

The Investigator will communicate his results with other participants and healthcare providers through the publication of the protocol and the research final results and recommendations. This will be done through publication websites and journals concerned with Oral and Maxillofacial Radiology specialty, For Sharing the recommended clinical application obtained from the final results of the research.

III- Appendix:

1- Epworth Sleepiness Scale (ESS):

Epworth Sleepiness Scale

Name: _____ Today's date: _____

Your age (Yrs): _____ Your sex (Male = M, Female = F): _____

How likely are you to doze off or fall asleep in the following situations, in contrast to feeling just tired?

This refers to your usual way of life in recent times.

Even if you haven't done some of these things recently try to work out how they would have affected you.

Use the following scale to choose the **most appropriate number** for each situation:

- 0 = would never doze
- 1 = slight chance of dozing
- 2 = moderate chance of dozing
- 3 = high chance of dozing

It is important that you answer each question as best you can.

Situation	Chance of Dozing (0-3)
Sitting and reading	_____
Watching TV	_____
Sitting, inactive in a public place (e.g. a theatre or a meeting)	_____
As a passenger in a car for an hour without a break	_____
Lying down to rest in the afternoon when circumstances permit	_____
Sitting and talking to someone	_____
Sitting quietly after a lunch without alcohol	_____

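### The bias section declares the study free of bias because CBCT readers are masked, but nothing masks the scoring of the 3-month sleep study behind AHI reduction, the outcome the trial is sized on

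*Combined protocol and SAP*

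**What the plan says.** All references are to the combined protocol and SAP.

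- **C) Variables, 3. Addressing potential sources of bias.** The section consists of a declaration and one measure: "No source of bias. CBCT images will be interpreted by three oral and maxillofacial radiologists independently blinded". The readers are masked to patient demographics, to the DISE findings and to one another's results.
- **C) Variables, 2. Data sources and management.** The same reading is tied to a particular outcome: "For the second outcome, CBCT images will be interpreted by three oral and maxillofacial radiologists independently".
- **D) Study size.** The aim and the sample size rest on a different outcome: "This study aims to assess surgical improvement in OSA patients after imaging of upper Respiratory Airway using CBCT and DISE using mean AHI reduction percentage". The same variable, "Mean AHI reduction percentage", stands first in the list in C.1.
- **B) Participants, Follow up.** That outcome comes from a repeat recording. Patients "will perform another sleep study after 3 months from the day of the surgery", and then "Percentage of AHI reduction will be calculated which in turn indicates post-surgical improvement". Nothing is said about who scores the recording, by what method, or with what knowledge of the arm.
- **A) Study design and setting, 1.** Only the study group has CBCT, and there the choice of procedure uses CBCT together with DISE.
- **B.2 Matching criteria and allocation ratio.** The main investigator generates the sequence, enrols and assigns. Opaque sealed envelopes are used.
- **II.d Confidentiality.** "All reports, data, scans, and administrative forms will be identified by a coded ID (identification) number only", with participant confidentiality as the stated purpose.

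**The concern.** The bias section makes a claim about the whole study and supports it with a safeguard on one secondary reading. The masked readers never see a control patient, because control patients have no scan. Their masking matters for the agreement of CBCT findings with DISE and for reader reliability, but it has no bearing on the difference between arms in AHI reduction.

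That difference depends on the sleep study 3 months after surgery. If the person who scores it, or who extracts the AHI, knows the arm and leans towards one side, the shift adds directly to the estimated treatment difference. No later analysis can separate it from a true effect. Prevention is possible only in the conduct of the trial, so the plan should either provide it or state that it is absent. As written, it does neither and says that no bias exists.

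**Working it through.** **Step 1. Which outcome decides the trial?** The documents do not attach the word primary to any outcome, so this is an inference. AHI reduction is the stated aim and the basis of the sample size (D), stands first in the variable list (C.1), and is the measure said to show post-surgical improvement (B, Follow up). The CBCT readings are called the second outcome and secondary outcomes (C.2). The inference is firm.

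**Step 2. Which safeguards reach that outcome?**

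| Safeguard in the plan | Where | What it protects | Reaches 3-month AHI scoring? |
|---|---|---|---|
| Masked CBCT readers | C.2, C.3 | Second outcome, study arm only | No |
| Computer-generated numbers, sealed envelopes | B.2 | Allocation | No |
| Coded IDs | II.d | Confidentiality | Not as written; nothing withholds arm or surgical details from the scorer |

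**Step 3. Who can know the arm?** Patients know whether they were scanned, and those deciding on surgery in the study group use the scan. The plan does not say this outright, but it follows from A.1. The main investigator knows the assignments (B.2). The plan neither connects any of these people with the scoring nor separates them from it.

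**Step 4. What would a differential shift do?** This is an illustration; the size of the shift is an assumption.

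Inputs from section D: difference 21.6, alpha 0.05, power 80%, 35 per group. No SD is given and sidedness is not stated, so 35 per group cannot be reproduced from the plan's own figures. Solving for the SD instead:

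- Normal approximation, two-sided: SD = 21.6 / [(1.960 + 0.842) × √(2/35)] = 32.3.
- Noncentral t, two-sided, 68 degrees of freedom: SD = 31.8. Check: SE = 31.8 × √(2/35) = 7.60, noncentrality 21.6/7.60 = 2.84, power 0.80.
- Normal approximation, one-sided: SD = 36.3.

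With no true effect and a shift b between arms, the two-sided t-test rejects with probability P(|T| > 1.995), where T is noncentral t with 68 degrees of freedom and noncentrality b/SE, SE = SD × √(2/35). SDs of 25 and 40 are taken as an assumed range around the back-calculated value.

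| Shift b (percentage points of AHI reduction) | SD 25 (SE 5.98) | SD 31.8 (SE 7.60) | SD 40 (SE 9.56) |
|---|---|---|---|
| 0 | 0.05 | 0.05 | 0.05 |
| 2.5 | 0.07 | 0.06 | 0.06 |
| 5 | 0.13 | 0.10 | 0.08 |
| 10 | 0.38 | 0.25 | 0.18 |

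For scale, 5 and 10 points are 5/21.6 = 23% and 10/21.6 = 46% of the difference the trial is designed to detect. At SD 31.8, shifts of 1 and 2 points give 0.052 and 0.058.

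**The case against.** The strongest reply is that AHI comes from an instrumented recording and may be little affected by who scores it. The documents do not say whether scoring is manual or automated, or that it involves judgement. This stands: how open the outcome is to such bias is an assumption. It limits the size of the concern. It does not rescue the declaration in C.3, because the plan gives no scoring rule, automation or independent scorer that would make masking unnecessary.

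A second reply is that a slight lean would do little harm. That is also right: at SD 31.8, shifts up to 2.5 points leave the false-positive rate at about 0.06. The larger figures need shifts of a quarter to a half of the design difference.

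A third is that the baseline study needs no new masking. This stands too. A.1 makes the baseline sleep study part of selection and B.2 places allocation after the pre-surgical examination, so baseline AHI is recorded before an arm exists. The gap concerns the 3-month study.

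A fourth is that the plan has bias controls outside C.3, namely random numbers and sealed envelopes. It does, but they act on allocation and not on outcome assessment.

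A reader might also infer from the main investigator's several roles that this person holds the data and could influence the AHI values. The documents do not support that. II.f gives access to the final data set to the investigator and the supervisors alike, and no section links the main investigator to sleep-study scoring.

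**Conclusion.** The concern holds in limited form. The declaration in C.3 is unsupported for percentage AHI reduction, because its only safeguard acts on a one-arm secondary reading and no section masks, or even identifies, the scorer of the 3-month sleep study. This rests on the text and on the inference that AHI reduction is the main outcome; it does not depend on the arithmetic.

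The size is illustrative. Under a two-sided 5% t-test with 35 per arm and no true effect, the false-positive rate would be about 0.06, 0.10 or 0.25 for shifts of 2.5, 5 or 10 points at SD 31.8. Across SDs of 25 to 40, a 5-point shift gives 0.13 to 0.08 and a 10-point shift 0.38 to 0.18. The SD is back-calculated and the shifts are assumed.

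A reader might go further and infer that AHI will be scored in favour of the CBCT arm, or that the trial's result would be invalid. The documents do not support either: they are silent on how scoring is done, and a masked scorer may in practice be used. The change should be made because the gap lies on the deciding outcome and cannot be repaired after the data are collected.

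**What to change.** Replace the opening declaration in C.3 with text such as: *The 3-month sleep study is passed on under the coded ID without arm, CBCT or surgical details and is scored by a person masked to arm. AHI values, including the baseline value recorded before allocation, are locked before they are linked to the allocation list. Patients and surgeon are not masked.* Keep the sentence on CBCT readers, and say that it applies to the CBCT outcomes.

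Name the scorer by role and state the scoring method, since the plan gives neither.

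The change needs no added patients, visits or recordings and no re-scoring of baseline studies, and the coded IDs are already planned. The downside is a little handling effort to strip arm and surgical details from the 3-month sleep-study request.
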